# 4.5.2.1. Paediatric Incontinence Questionnaire (PinQ)

The PinQ will be used to assess the child's QoL. The PinQ is a validated cross-cultural continence-specific paediatric QoL questionnaire to assess children with bladder dysfunction, developed by Bower et al. (Bower et al. 2006). It is available as self-rated and proxy versions. This will be completed by the child themselves in the older participant group and will be completed by the parent/carer on behalf of the child in the younger participant group.

The PinQ measures the emotional impact that urinary incontinence has on a child. It consists of 20 urinary incontinence QoL related questions divided in 2 dimensions: intrinsic (14 items) and extrinsic (6 items), which are graded on a scale of 0 to 4 (0=No, 1=Hardly ever, 2=Sometimes, 3=Often, 4=All the time) with a total possible global score of 80.

The total score indicates the impact urinary incontinence has on the child's QoL with the higher scores indicating a more significant effect.

# 4.5.2.2. World Health Organization Quality of Life (WHOQOL) BREF

The WHOQoL-BREF questionnaire (WHO 1996) will be used to assess the parents'/carers' QoL. It will be completed directly by the parent/carer. A general QoL question will be added to the end of the survey, specifically asking their perspectives on how the current management

of their child's NE affects their QoL. The WHOQoL-BREF questionnaire is derived from a larger instrument, the WHOQoL-100. It includes 26 items, grouped in 4 domains: Physical Heath, Psychological, Social Relationships, and Environment, and 2 separate items asking the respondent about overall perception of QoL (item 1) and an individual's overall perception of their health (item 2). It is available in self-rated or interview-based forms.

The scores of items 3, 4 and 5, which are negatively phrased, need to be reversed. The mean score of items within each domain is used to calculate the domain scores, which are converted into a 0-100 scale. Higher scores denote higher QoL.

Where more than 20% of data is missing from an assessment, the assessment should be discarded. Where an item is missing, the mean of other items in the domain is substituted. Where more than 2 items are missing from the domain, the domain score should not be calculated (except for domain 3 [Social relationships], where the domain should only be calculated if <1 item is missing).

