4.3 Changes to Analysis from Protocol

Concomitant medications will be collected in relation to adverse events and medical device incidents only. For this reason, the summary of concomitant medication will be provided on randomised analysis set only as no data will be collected for patients screened and not randomised.

Document:	Y:\Kimberly-Clark\DryNites\Documentation\SAP\DryNites_SAP_v1.0_20200203		
Author:	[name] Version Number:		1.0
		Version Date:	03Feb2020
Template No.: RWI_TP_BIOS0013 Revision 1			Reference: RWI_WI_BIOS0015
Effective Date: 15Jun2018			

Safety set definition will be modified to include all patients exposed to DryNites for at least 1 night after signature of informed consent.

Treatment emergent adverse events will be defined as all events occurred or worsened in severity after the start of the screening period.

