15.2.1.2 WHOQoL-BREF

The WHOQoL-BREF questionnaire (WHO 1996) assesses the individual's perceptions in the context of their culture and value systems, and their personal goals, standards and concerns. It comprises 26 items, which measure the following broad domains: physical health (items 3, 4, 10, 15, 16, 17 and 18), psychological health (items 5, 6, 7, 11, 19 and 26), social relationships (items 20, 21 and 22), and environment (items 8, 9, 12, 13, 14, 23, 24 and 25). There are also 2 items that are examined separately: item 1 asks about individual overall perception of quality of life and item2 asks about individual overall perception of their health.

Domain scores are scaled in a positive direction (i.e. higher scores denote higher QoL). The scores of items 3 ("To what extent do you feel that physical pain prevents you from doing what you need to do?"), 4 ("How much do you need any medical treatment to function in your daily life?") and 26 ("How often do you have negative feelings such as blue mood, despair, anxiety, depression?"), which are negatively phrased, will be reversed.

Document:	Y:\Kimberly-Clark\DryNites\Documentation\SAP\DryNites_SAP_v1.0_20200203		
Author:	[name]	Version Number:	1.0
		Version Date:	03Feb2020
Template No.:	RWI_TP_BIOS0013 Revision 1		Reference: RWI_WI_BIOS0015
Effective Date:	15Jun2018		

The mean score of items within each domain will be used to calculate the domain scores. The mean will be then multiplied by 4 as to be directly comparable with scores derived from the WHOQOL-100. As last steps, the data transformation reported below will be applied to obtain a 0-100 score:

- Domain 1 to 4: (domain score 4)*100/16;
- Item 1 and 2: (items score -1)*100/4.

Higher scores denote higher QoL.

Where more than 20% of data is missing from an assessment, the assessment should be discarded. Where an item is missing, the mean of other items in the domain is substituted to the missing item score. Where more than 2 items are missing from the domain, the domain score should not be calculated (except for domain 3 [Social relationships], where the domain should only be calculated if <1 item is missing).

The 3 questions added at the end of the questionnaires will be listed only.

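### Protocol 4.5.2.2 reverses WHOQoL-BREF items 3, 4 and 5 but SAP 15.2.1.2 reverses 3, 4 and 26; the protocol list, if used, would mis-score the psychological domain

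*Protocol*

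**What the plan says.** Protocol 4.5.2.2, which describes the WHOQoL-BREF as an outcome measure, gives this reversal rule: "The scores of items 3, 4 and 5, which are negatively phrased, need to be reversed". It then says that domain scores are built from item means, converted to 0-100, and that "Higher scores denote higher QoL".

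SAP 15.2.1.2 gives the full derivation. It reverses items 3, 4 and 26 and prints the wording of each. Item 26 reads: "How often do you have negative feelings such as blue mood, despair, anxiety, depression". It assigns items to domains, including "psychological health (items 5, 6, 7, 11, 19 and 26") and "physical health (items 3, 4, 10, 15, 16, 17 and 18"). Items 5 and 26 are therefore both in the six-item psychological domain, and items 3 and 4 are in the physical domain. Item 5's wording appears in neither document.

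Protocol Table 1 sets change from baseline in each domain score at Day 56 as the secondary endpoint for the parent's quality of life. Protocol 5.4.2 describes the domain scores again but gives no reversal list. Protocol 5.4.1 leaves the full description of the analysis to the SAP. SAP 4.3, which lists departures from the protocol, covers concomitant medication, the safety set and the definition of treatment-emergent events, and does not mention WHOQoL-BREF scoring.

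**The concern.** The two lists cannot both be applied, and the documents themselves show which one fails. On the printed wording of item 26, a higher raw answer means more frequent low mood or anxiety. Unless the item is reversed, a parent who feels worse scores higher, against the direction both documents require. The protocol list omits item 26. It also reverses item 5, which the SAP leaves as answered.

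The trial aims to show that absorbent pants improve the parent's quality of life. If the psychological domain were scored by the protocol list, items pointing the wrong way would offset the rest and shrink any real difference between groups. The mismatch is also undeclared: protocol version 3.0 (28 January 2022) postdates the SAP (3 February 2020) and still carries 3, 4 and 5. A later reader could dispute which rule was pre-specified.

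**Working it through.** The plan gives no figure to reproduce here, so the check scores the domain under each list.

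**Inputs**
- Psychological items: 5, 6, 7, 11, 19, 26 (SAP 15.2.1.2).
- Reversal lists: {3, 4, 5} in the protocol, {3, 4, 26} in the SAP.
- Scaling: "The mean will be then multiplied by 4 as to be directly comparable with scores derived from the WHOQOL-100". The 0-100 score is then (domain score − 4) × 100/16. The minus sign is lost in the extracted text, but the domain score runs from 4 to 20, which fits this reading.
- Item range 1 to 5, implied by the single-item transformation ("items score -1)*100/4"). A reversed item is therefore 6 − x.
- Direction: item 26 is negative (printed wording). Item 5 is taken as positive because the SAP does not reverse it (inferred).

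**Formula.** The score is (mean × 4 − 4) × 100/16 = (mean − 1) × 25, so one item point is worth 25/6 = 4.17 points.

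**Uniform one-category improvement on all six items**
- SAP list: 6/6 × 25 = 25 points.
- Protocol list: four items rise by 1, and items 5 and 26 each fall by 1. (4 − 2)/6 × 25 = 8.3 points, one third.
- Only item 26 wrong: (5 − 1)/6 × 25 = 16.7 points, two thirds.

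**Scores when every item is at the same favourable level (1 worst, 5 best)**

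| Level | SAP list | Protocol list | Only item 26 wrong |
|---|---|---|---|
| 1 | 0 | 33.3 | 16.7 |
| 2 | 25 | 41.7 | 33.3 |
| 3 | 50 | 50 | 50 |
| 4 | 75 | 58.3 | 66.7 |
| 5 | 100 | 66.7 | 83.3 |

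Over all answers to items 5 and 26, the difference between the two lists in one parent's score runs from −33.3 to +33.3 points.

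**Standardised effect.** Assume the same shift and the same SD for each item, and a common inter-item correlation ρ (an assumption; the documents give none). The ratio of protocol to SAP effect is (1/3) × √[(6 + 30ρ)/(6 − 2ρ)].
- ρ = 0.3: (1/3) × √(15/5.4) = 0.56.
- ρ = 0.6: (1/3) × √(24/4.8) = 0.75.

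**When the sign would change.** In favourable-direction units, the protocol list gives the summed change on the other four items minus the summed change on items 5 and 26. It cancels a true improvement only if those two items together improve as much as the other four together, and reverses it only if they improve more.

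**Other domains.** Items 3 and 4 are reversed under both lists, so the physical domain is identical. The social and environment domains contain none of items 3, 4, 5 or 26.

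**The case against.** The strongest reply is that the correct rule already sits where the scoring is done. Protocol 5.4.1 defers to the SAP, and the protocol never assigns WHOQoL-BREF items to domains, so nobody could score the domains from the protocol alone. This stands, and it makes the harm conditional. A reader might infer that version 3.0 overrides the SAP because it is later. The documents do not support that: the protocol itself points to the SAP for the analysis.

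Second, item 5's wording is not printed, so two wrongly directed items are not proven from the documents; one is. This also stands, and is why the one-item result is given beside the two-item result. The defect survives on item 26 alone.

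Third, a reader might illustrate the size with a single parent. With item 5 = 4 and item 26 = 2, the two items contribute 4 + 4 under the SAP and 2 + 2 under the protocol, a gap of 4/6 × 25 = 16.7 points. The arithmetic is right, but this is a shift in level. The endpoint is change from baseline, and a parent who gives the same answers at both visits has no error in change.

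Fourth, a reader might infer that the effect could well be cancelled or reversed. That needs an effect concentrated on items 5 and 26, and nothing in the documents suggests one.

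Finally, SAP 8.1 plans no confirmatory testing, SAP 15.2.3.1 labels these p-values exploratory, and item-level data are retained, so any mis-scoring could be recomputed. All of this limits the consequence. None of it makes the protocol sentence right.

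**Conclusion.** The contradiction is real, and the protocol list is the faulty one for the psychological domain. If it were used, a uniform improvement would be cut to one third (8.3 points instead of 25), or to two thirds (16.7) if only item 26 is counted as wrong. The harm shown is attenuation of one of four domain scores; Table 1 covers this domain through its reference to each domain and does not single it out. The physical, social and environment scores, the primary endpoint and the sample size are untouched, and an analysis programmed from the SAP is not affected.

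The result rests on the SAP's item lists and scaling, on higher raw answers to item 26 meaning more frequent negative feelings, and, for the two-item figure, on item 5 being positively phrased.

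A reader might also fault SAP 4.3 for not declaring the difference. That criticism is weak. Its entries concern other matters (for example, "Safety set definition will be modified to include all patients exposed to DryNites"), and the SAP is based on protocol version 1.0, which is not available, so it cannot be known whether there was a difference to declare at that time.

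**What to change.** Correct Protocol 4.5.2.2 so that the reversed items are 3, 4 and 26, matching SAP 15.2.1.2. When doing so, check the wording of item 5 against the questionnaire listed among the stand-alone documents in Protocol section 10, since the choice for that item currently rests on the SAP alone. Confirm that the scoring program uses the SAP list. Once the protocol is corrected, SAP 4.3 has no departure to record; an entry there is needed only if the protocol stays as it is. The cost is a one-line protocol correction and a short check of the code. No data collection or sample size changes.

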# 4.5.2.3. Paediatric Daytime Sleepiness Scale (PDSS)

The PDSS questionnaire will be used to assess the child's sleep. It is comprised of 8 items assessing daytime sleepiness and rated on a 5-point Likert scale ranging from 4 (Always/Very often) to 0 (Never); the score of the third item needs to be reversed to calculate the total score. Higher scores indicate greater daytime sleepiness, and were associated with reduced total sleep time, poorer school achievement, poorer anger control, and frequent illness. The scale score is correlated with total hours of night-time sleep (Drake et al. 2003). While no time reference is specifically identified by the questionnaire, items query feelings of drowsiness in a variety of settings over the course of the day. It is validated for administration in children 5-17 years old. This will be completed by the child themselves (with attendance of an adult) in the older participant group and will be completed by the parent/carer on behalf of the child in the younger participant group.

At enrolment, the site will record whether the child takes regular daytime naps; these children will be excluded from the analyses of sleep.

# 4.5.2.4. Checklist Individual Strength (CIS)

The CIS questionnaire will be used to assess the parents' sleep. This will be completed directly by the parent/carer.

The CIS consists of 20 statements on fatigue-related problems respondents might have experienced in the past 2 weeks. A Likert scoring scheme from 1 to 7 is used. The questionnaire covers measures 4 dimensions of fatigue: Subjective fatigue severity (8 items), Concentration problems (5 items), Reduced motivation (4 items) and Physical activity (3 items). It yields 1

total score and 4 domain scores. On the fatigue severity subscale, a cut-off score of 35 is seen as indicative of severe fatigue. In a study on work absence due to fatigue, a cut-off score of 76 on the CIS indicates a risk for subsequent sick leave or work disability (Bültmann et al. 2000).

# 4.5.2.5. Absorbent Pants and DryNites® Clinical Trial Questionnaires

The child and parents'/carers' perspectives on their experience with previous absorbent pants/nappies, and on the attributes of DryNites® vs. previously used products will be recorded via 2 specific questionnaires designed for this study and administered at study entry (Absorbent Pants Clinical Trial Questionnaire, about previous products) and at Day  $28 \pm 7$  (DryNites® Clinical Trial Questionnaire).

Each questionnaire includes the following: identification of previous absorbent product (question 1), 2 narrative questions, 11 statements about the absorbent product (responses: Agree, Tend to agree, Neither agree nor disagree, Tend to disagree, Disagree). The Absorbent Pants Clinical Trial Questionnaire includes 6 questions on the attributes of the previous absorbent product, responded on a 1-10 scale (with 1= not at all, and 10 being the highest level of appreciation). The DryNites® Questionnaire includes an overall preference question, responded on a 1-10 scale, and 8 specific questions on preference for DryNites® attributes compared to the previous absorbent product.

### 4.5.3. Other Assessments

#### 4.5.3.1. Willingness to Continue in the Extension Period

If the child or parents/carers do not wish to participate in the extension trial, their reasons for non-participation will be recorded in the eCRF on Day  $56 \pm 7$ .

# 4.5.3.2. Physical Examination

The baseline visit can be performed remotely.

In case of on-site baseline visit, a complete physical examination will be performed to confirm eligibility for enrolment, with special attention to the external genitalia and the lower back region to exclude any pathology that may cause incontinence in children. It will have 3 components (Haid et al. 2017):

Body height and body weight, and calculation of the body mass index (BMI). This
may detect any issue regarding failure to thrive, growth retardation or the presence
of obesity

- External genitalia examination of urethral meatus to exclude epispadias; hypospadias; meatal stenosis; phimosis; labial adhesions
- Examination of the lower back for dimples, hypertrichosis, or a suspect palpatory finding, to possibly point to spina bifida occulta. In addition, an orienting neurological examination (sensitivity, walking pattern) and inspection of the feet (looking for malformations such as clubbing, tight heel cords, and toe mispositioning in patients with neurogenic bladder-emptying disorders) will be performed. Testing the grasp function of the toes is a simple neurological test for an intact S1-S2-S3 innervation.

In case a remote visit is performed, height/weight and full physical examination will not be recorded. In this scenario, the Investigator must check the medical records and/or interview the parent/carer to investigate history of congenital abnormalities of the urinary tract, history of surgery on the urinary tract, and history of verified urinary tract infections before determining eligibility.

#### 4.6. Adverse Events

The definitions, recording and reporting of an AE, SAE or Medical Device Incident can be found in Section 7.

Adverse events will be reported by the participant, parents/carers, or the participant's legally authorised representative.

The Investigator and any designees are responsible for detecting, documenting, and recording events that meet the definition of an AE or SAE and remain responsible for following-up AEs that are serious, considered related to the study treatment or study procedures, or that caused the patient to discontinue the study treatment.

Care will be taken not to introduce bias when detecting AEs and/or SAEs. Open-ended and non-leading verbal questioning of the participant is the preferred method to inquire about AE occurrences.

Documentation regarding the AE should be made as to the nature, date of onset, end date, severity, relationship to product, action(s) taken, and outcome of any sign or symptom observed by the physician or reported by the patient/parents/carers upon indirect questioning.

# **4.6.1.** Time Period and Frequency for Collecting Adverse Event and Serious Adverse Event Information

All AEs will be collected from the date of written informed consent granted by the parent(s)/carer(s) onwards until discontinuation of the study at the time points specified in the schedule of assessments.

All SAEs will be recorded in the eCRF within 24 hours of awareness; this will trigger an immediate email notification of the SAE to the Sponsor. The Investigator will record any updated SAE data in the eCRF within 24 hours of it being available; this will trigger an email notification of the SAE follow-up report to the Sponsor accordingly.

Investigators are not obligated to actively seek AE or SAE after conclusion of the study participation. However, they will follow-up any AE ongoing at study discontinuation until resolution or stabilisation.

#### 4.6.2. Follow-up of Adverse Events and Serious Adverse Events

After the initial AE/SAE report, the Investigator is required to proactively follow each participant at subsequent visits/contacts. All AEs will be followed until resolution, stabilisation, the event is otherwise explained, or the participant is lost to follow-up.

## 4.6.3. Regulatory Reporting Requirements for Serious Adverse Events

- Prompt notification by the Investigator to the Sponsor of an SAE is essential so that legal obligations and ethical responsibilities towards the safety of participants and the safety of a study treatment under clinical investigation are met.
- The Sponsor has a legal responsibility to notify both the local regulatory authority and other regulatory agencies about the safety of a study treatment under clinical investigation. The Sponsor will comply with country-specific regulatory requirements relating to safety reporting to the regulatory authority, Institutional Review Boards (IRB)/Independent Ethics Committees (IEC), and Investigators.
- Investigator safety reports must be prepared for suspected unanticipated serious adverse device effect (USADE) according to local regulatory requirements and Sponsor policy and forwarded to Investigators as necessary.
- An Investigator who receives an Investigator safety report describing an SAE or
  other specific safety information (e.g., summary or listing of SAEs) from the
  Sponsor, will review and then file it along with the Investigator's Brochure and will
  notify the IRB/IEC, if appropriate according to local requirements.

#### 4.6.4. Medical Device Incidents (Including Malfunctions)

Medical devices are being provided for use in this study for the purpose of NE. In order to fulfil regulatory reporting obligations worldwide, the Investigator is responsible for the detection and

documentation of events meeting the definitions of incident or malfunction that occur during the study with such devices.

A Medical Device Incident is an event that causes, or has the potential to cause, unexpected or unwanted effects involving the health and safety of patient's, users or other persons.

## 4.6.4.1. Time Period for Detecting Medical Device Incidents

- Medical Device Incidents or malfunctions of the device that result in an incident will be detected, documented, and reported during all periods of the study in which the medical device is used.
- If the Investigator learns of any incident at any time after a patient has been discharged from the study, and such incident is considered reasonably related to a medical device provided for the study, the Investigator will promptly notify the Sponsor.

## 4.6.4.2. Follow-up of Medical Device Incidents

- All Medical Device Incidents involving an AE will be followed and reported in the same manner as other AEs (see Section 4.6.2). This applies to all patients, including those who discontinue study treatment.
- The Investigator is responsible for ensuring that follow-up includes any supplemental investigations as indicated to elucidate the nature and/or causality of the incident.
- New or updated information will be recorded on the originally completed form with all changes signed and dated by the Investigator.

## 4.6.4.3. Prompt Reporting of Medical Device Incidents to Sponsor

- Medical Device Incidents will be reported to the Sponsor within 24 hours after the Investigator determines that the event meets the clinical investigation plan definition of a Medical Device Incident.
- The Medical Device Incident Report Form will be completed in the eCRF using the SAE form. This will trigger an immediate email notification of the Medical Device Incident to the Sponsor.

• The same individual will be the contact for the receipt of Medical Device Incident reports and SAE reports.

